## **Efficacy**

The number of patients experiencing suppression of Epstein-Barr virus in the two groups will be compared using Chi-Square test (or Fisher's exact if appropriate) followed by logistic regression adjusting for baseline FEV1 and other covariates if required. The odds ratio and 95% confidence interval will be reported.

The intention-to-treat basis analysis will use a significance level of  $\leq 0.05$  for the primary outcome. Per-protocol analysis will also be conducted which will involve a comparison of treatment groups that includes patients with overall study drug adherence of at least 70%. Subgroup analyses will be performed on the primary outcome for compliance. In order to assess differences in treatment effects between the subgroups we will report odds ratio and 99% CI from the treatment\*subgroup interaction model. Sensitivity analysis will be performed for the primary efficacy outcome excluding patients with a confirmed diagnosis of COVID-19

Additionally, change in viral load (Quantitative PCR) from baseline to week 8 in the two groups will be compared using independent t-test (or non-parametric alternative). The mean difference and 95% confidence interval will be reported.

### **7.2 Analysis of secondary, exploratory and other safety outcomes**

The lung function outcomes will be reported using Mean (SD) or Median (p25 to p75) in patients with COPD. The change in lung function from baseline to week 8 in the two groups will be analysed using independent t-test or non-parametric alternative. The mean at baseline versus the mean at week 8 within each group will be analysed using a paired t-test or non-parametric alternative.

Exploratory subgroup analyses will be performed on the lung function outcomes for EBV suppression. Analysis of Covariance will be used to assess differences in

treatment effects between the subgroups and will be reported using mean difference and 99% CI.

Tolerability of valaciclovir will be assessed by measuring participant compliance at visit 2 and 3. The compliance (%) will be reported using mean (SD) or Median (p25 to p75) and will be analysed using independent t-test or non-parametric alternative

The change over time in CAT score and EQ-5D will be reported using Mean (SD) or Median (p25 to p75). The change from baseline to 8 weeks will analysed using independent t-test or non-parametric alternative.

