## **7. ANALYSIS PRINCIPLES**

The comparison of continuous outcomes will be carried out using t-tests followed by analysis of covariance adjusting for baseline FEV1 and other covariates if required. The mean and 95% confidence intervals will be reported. The categorical variables will be analysed using Fisher's Exact test or Chi-square test followed by logistic regression adjusting for baseline FEV1 and other covariates if required. The odds ratio and 95% confidence will be reported.

Statistical diagnostic methods will be used to check for violations of the assumptions, and transformations will be performed where required. Analyses will be on an intention-to-treat basis and all statistical tests will be at the 2-sided p-value of 0.05. A single final analysis is planned at the end of the trial.

Every effort will be made to minimise missing baseline and outcome data in this trial. The level and pattern of the missing data in the baseline variables and outcomes will be established by forming appropriate tables and the likely causes of any missingness will be investigated. This information will be used to determine whether the level and type of missing data has the potential to introduce bias into the analysis results for the proposed statistical methods, or substantially reduce the precision of estimates related to treatment effects. If necessary, these issues will be dealt with using multiple imputation or Bayesian methods for missing data as appropriate.

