  - Change in FEV1/FVC ratio from baseline to week 8, mean(SD) by treatment arm, difference in mean with 95% CI
    - Exploratory Subgroup Analysis\*: EBV Suppression (as defined by 90% reduction in viral load) (Yes, No), mean(SD) by treatment arm, difference in mean and interaction term from ancova with 99% CI
  - Change in MMEF from baseline to week 8, mean(SD) by treatment arm, difference in mean with 95% CI
    - Exploratory Subgroup Analysis\*: EBV Suppression (as defined by 90% reduction in viral load) (Yes, No), mean(SD) by treatment arm, difference in mean and interaction term from ancova with 99% CI
  - Change in PEF from baseline to week 8, mean (SD) by treatment arm, difference in mean with 95% CI
    - Exploratory Subgroup Analysis\*: EBV Suppression (as defined by 90% reduction in viral load) (Yes, No), mean(SD) by treatment arm, difference in mean and interaction term from ancova with 99% CI
  - Exploratory Subgroup Analysis\*: EBV Suppression (as defined by 90% reduction in viral load) (Yes, No), mean(SD) by treatment arm, difference in mean and interaction term from ancova with 99% CI
  - Change in TLCO from baseline to week 8, mean(SD) by treatment arm, difference in mean with 95% CI

- Exploratory Subgroup Analysis\*: EBV Suppression (as defined by 90% reduction in viral load) (Yes, No), mean(SD) by treatment arm, difference in mean and interaction term from ancova with 99% CI
  - Descriptive statistics for lung function including; FEV1, FEV1 as a percentage of the predicted FEV1 value, FVC, FEV1/FVC Ratio, MMEF, PEF and TLCO at baseline, week 4 and week 8, mean(SD) or median (IQR) by treatment arm.
  - Difference between lung function measures at baseline and week 8 in the active and placebo groups separately for all lung function outcomes, mean (SD) within each treatment arm, mean difference and 95% CI
- Participant compliance measured by total number of tablets administered as a proportion of total number of tablets supplied, mean(SD) by treatment arm, mean difference and 95% CI
- **Exploratory Outcomes**
  - Clinical
    - Symptoms measured by CAT score and EQ-5D-5L from baseline to week 8, n(%) by treatment arm, mean difference and 95% CI
      - Descriptive statistics will also be presented at baseline, week 4 and week 8, mean(SD), median (IQR) or n(%) by treatment arm.
    - Suppression of Epstein-Barr virus in the sputum of subjects with COPD from baseline to week 4, n(%) by treatment arm, odds ratio and 95% CI\*

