**Table x.x: Paired analysis for lung function in active and placebo groups**

		Valaciclovir N = <n>	Difference (95% CI)	P value	Placebo N = <n>	Difference (95% CI)	P value
Forced Expiratory Volume (FEV1 (L))	Baseline	xx.x (x.x)	xx.x (xx.x – xx.x)	0.xx	xx.x (x.x)	xx.x (xx.x – xx.x)	0.xx
	Week 8	xx.x (x.x)			xx.x (x.x)		
Forced Expiratory Volume in 1 second (FEV1 as a percentage of the predicted FEV1 value (%))	Baseline	xx.x (x.x)	xx.x (xx.x – xx.x)	0.xx	xx.x (x.x)	xx.x (xx.x – xx.x)	0.xx
	Week 8	xx.x (x.x)			xx.x (x.x)		
Forced Vital Capacity (FVC (L))	Baseline	xx.x (x.x)	xx.x (xx.x – xx.x)	0.xx	xx.x (x.x)	xx.x (xx.x – xx.x)	0.xx
	Week 8	xx.x (x.x)			xx.x (x.x)		
Mid Expiratory Flow (MMEF 25-75% (L/s))	Baseline	xx.x (x.x)	xx.x (xx.x – xx.x)	0.xx	xx.x (x.x)	xx.x (xx.x – xx.x)	0.xx
	Week 8	xx.x (x.x)			xx.x (x.x)		
Peak Expiratory Flow (PEF (L/s))	Baseline	xx.x (x.x)	xx.x (xx.x – xx.x)	0.xx	xx.x (x.x)	xx.x (xx.x – xx.x)	0.xx
	Week 8	xx.x (x.x)			xx.x (x.x)		
FEV1/FVC Ratio (%)	Baseline	xx.x (x.x)	xx.x (xx.x – xx.x)	0.xx 0.xx	xx.x (x.x)	xx.x (xx.x – xx.x)	0.xx

	Week 8	xx.x (x.x)			xx.x (x.x)		
Transfer Factor (TLCO (as a percentage of the predicted value) (%))	Baseline	xx.x (x.x)	xx.x (xx.x – xx.x)	0.xx	xx.x (x.x)	xx.x (xx.x – xx.x)	0.xx
	Week 8	xx.x (x.x)			xx.x (x.x)		

Continuous outcomes reported as Mean (SD). Paired sample t-test used to determine if any difference between lung function measures at baseline and week 8 in the active and placebo groups separately.

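### Within-arm paired tests on seven lung-function measures are planned with p-values and no descriptive label, although they test change over time and not treatment

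*SAP*

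**What the plan says.** SAP 7.2 sets out two analyses of lung function. The first compares the arms: "The change in lung function from baseline to week 8 in the two groups will be analysed using independent t-test or non-parametric alternative". The second looks inside each arm: "The mean at baseline versus the mean at week 8 within each group will be analysed using a paired t-test or non-parametric alternative".

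SAP 8.4 gives the scope of the second analysis: "Difference between lung function measures at baseline and week 8 in the active and placebo groups separately for all lung function outcomes". The measures it lists are FEV1, FEV1 % predicted, FVC, FEV1/FVC, MMEF, PEF and TLCO. For the within-arm item, 8.4 itself asks only for mean (SD), mean difference and 95% CI.

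Appendix 1 goes further. The table titled "Paired analysis for lung function in active and placebo groups" gives each of the seven measures a difference, a 95% CI and a p-value for valaciclovir, and the same again for placebo. It has no column comparing the arms. Its footnote reads: "Paired sample t-test used to determine if any difference between lung function measures at baseline and week 8 in the active and placebo groups separately". The between-arm results are in a separate table of lung-function secondary outcomes.

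SAP 7 applies one threshold throughout: "all statistical tests will be at the 2-sided p-value of 0.05". It offers ANCOVA adjusting for baseline FEV1, but only if required. Protocol 13.2 describes t-tests followed by ANCOVA if required for continuous secondary and exploratory outcomes, and mentions no within-arm tests. SAP 8.4 stars several additions as not detailed in the protocol, but not this one.

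**The concern.** The treatment effect in a randomised trial is the difference between arms. Any change that both arms share over eight weeks, whatever its cause, counts towards significance in each paired test but cancels in the between-arm difference. One arm reaching p<0.05 while the other does not is therefore no evidence that the arms differ.

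The draft table sets the two arms' p-values side by side, tested at the same 0.05 level as everything else, with no caution. That layout invites the comparison the tests cannot support. What is at stake is a claim on the secondary objective (lung function): that patients improved on valaciclovir and not on placebo, when the randomised comparison may show nothing. Viral load, CAT and EQ-5D get only between-arm tests of change. Lung function alone gets the extra tests, and no reason is given.

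**Working it through.** The plan gives no power, SD or expected change for lung function, so there is no figure of its own to reproduce for these tests. The check asks how often the misleading pattern would arise if valaciclovir had no effect.

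**Inputs**
- Tests: 7 measures × 2 arms = 14 (SAP 8.4 and the Appendix 1 table).
- Level: two-sided 0.05 (SAP 7).
- n = 31 per arm. This is the evaluable number in Protocol 13.1 and SAP 5, sized for EBV suppression of 70% versus 30%. That figure reproduces: (1.960·√0.50 + 1.282·√0.42)² / 0.40² = 30.7, rounded up to 31. Using it for week-8 spirometry is an assumption.
- Shared mean change d, in SDs of the change score and equal in both arms: assumed, range 0 to 0.5.

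**One measure.** Let p be the probability that a paired t-test is significant: P(|T| > 2.042), where T is noncentral t with 30 df and noncentrality d√31. Let u be the part of p in the direction of improvement. The arms are independent, so

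- P(exactly one arm significant) = 2p(1−p)
- P(significant improvement on valaciclovir, placebo not significant) = u(1−p)

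| d | d√31 | p | u | 2p(1−p) | u(1−p) |
|---|---|---|---|---|---|
| 0 | 0 | 0.050 | 0.025 | 9.5% | 2.4% |
| 0.2 | 1.114 | 0.190 | 0.189 | 30.8% | 15.3% |
| 0.35 | 1.949 | 0.471 | 0.471 | 49.8% | 24.9% |
| 0.5 | 2.784 | 0.7685 | 0.7685 | 35.6% | 17.8% |

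The function 2p(1−p) peaks at 50% when p = 0.5, so discordance rises and then falls as the shared change grows. The number of patients moves the curve:
- At 44 per arm, d = 0.2 gives p = 0.254 and 38% discordance; d = 0.5 gives p = 0.900 and 18%.
- At 20 per arm, d = 0.2 gives p = 0.136 and 23.5%; d = 0.5 gives p = 0.5645 and 49%.

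In simulation (20,000 replicates) the between-arm test stayed at about 5% per measure for every d.

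**All 14 tests, no change in either arm.** If independent, P(at least one p<0.05) = 1 − 0.95¹⁴ = 51%. The measures are not independent: FEV1 appears in litres and as % predicted, and FEV1/FVC is built from two others. At an assumed correlation of 0.8, simulation gives 28%. These figures count any significant result, in either arm and either direction.

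**Seven measures, at least one improved-on-valaciclovir-only result** (simulated, 31 per arm; ranges run from correlation 0.8 to 0): 7% to 15% at d = 0, and 34% to 68% at d = 0.2. For comparison, the chance of at least one significant between-arm result in either direction, across the same seven measures, is about 15% to 30% at both values of d. The paired tests therefore add little risk of a false claim when nothing changes in either arm. They add a good deal once there is a modest shared change.

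**The case against.** The strongest reply is that the correct analysis is already planned. The between-arm test comes first in 7.2, each measure has a between-arm difference with CI in 8.4, and the appendix gives those results their own table with p-values. The paired table is separate and accurately titled, and its footnote says the arms are analysed separately. All of this stands. A reader might infer that the SAP means to judge efficacy from the paired tests, or to use them in place of the randomised comparison. No passage says so. The misreading is a risk created by the presentation, not a stated inference.

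Three other strong readings also go beyond the documents:
- **That discordant p-values are likely.** The 50% figure is the top of a curve that starts at about 10%, and no passage supports one value of the shared change over another.
- **That few patients have week-8 spirometry.** SAP 2.2 and Protocol 5.3.2 say lung function will not be measured because of the lockdown. Neither says how many patients had already been measured.
- **That regression to the mean is to be expected in both arms because screening spirometry also determines eligibility.** The FEV1 criterion is a two-sided window (30–80% predicted), so regression at its two ends pulls in opposite directions. Several of the seven measures are not selection criteria at all. Neither the size nor the direction of any such effect can be read from the documents.

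It can also be said that these are supplementary p-values on a secondary outcome. That limits the weight of the point, but it is no reason to keep tests that do not address the objective.

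**Conclusion.** The point holds as a flaw of analysis and presentation. The SAP plans 14 within-arm p-values that do not estimate the treatment effect, gives them the same 0.05 threshold as the randomised comparison, and does not label them descriptive.

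With no treatment effect, the chance of significance in exactly one arm on a given measure is between about 10% and 50%. The chance of apparent improvement on valaciclovir alone is between about 2% and 25%. These ranges rest on an assumed 31 patients per arm and an assumed shared change of 0 to 0.5 SD, because the documents give neither the number with week-8 spirometry nor an SD. The 51% chance of at least one p<0.05 among the 14 tests is an upper figure that needs independence; 28% at correlation 0.8 is nearer to what such overlapping measures would give.

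The primary outcomes, the sample size and the planned between-arm comparison are unaffected. The change should be made because it is cheap and removes a misleading route to a claim on a secondary objective.

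**What to change.** 1. Delete the paired-test sentence in SAP 7.2.
2. In the Appendix 1 paired-analysis table, delete the two p-value columns and the footnote.
3. Keep the within-arm mean change (SD or CI) in 8.4 and the appendix, labelled as descriptive only. If the CI is kept the label is essential, because a 95% CI that excludes zero carries the same message as p<0.05. Star the item as not detailed in the protocol, as 8.4 does for other additions.
4. State that inference on lung function rests only on the between-arm difference from ANCOVA, adjusted for the baseline value of the same measure. This replaces the unadjusted t-test of change in 7.2. Adjusting for baseline FEV1, as SAP 7 allows, does not do this for TLCO, PEF and the rest.
5. Report the number with paired spirometry in each arm.

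The cost is a few lines of SAP text and one table shell. It needs no new data and no change to the sample size or patient care, and no information about the treatment effect is lost. Adjusting for baseline should generally improve precision over the test of change.

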### 10.1.3 Visit 2 (Week 4 +/- 7days) Procedures

Participants will undergo assessment via telephone call (including medication review and recording of adverse events). CAT and EQ-5D-5L assessments will be completed remotely via telephone call. Participants will be asked regarding exacerbation status and if applicable exacerbations will be documented. A sputum sample will be left for collection by the participant .Participants will count surplus medication and advise the researcher of the tablet count . A new 4-week supply of medication will be dispensed.

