### 2.3 Exploratory Outcomes

#### Clinical Exploratory Outcomes

- Symptoms measured by CAT score and EQ-5D-5L from baseline to week 8.

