## 5. SAMPLE SIZE CALCULATIONS

A sample size of 31 subjects per group will have 90% power at a two-tailed significance level of 0.05 to detect a difference in the exploratory efficacy outcome EBV shedding of 70% in the treated group to 30% in the control group. With a dropout rate of approximately 30%, this study will require a total of 44 patients per group.

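### CAT and EQ-5D-5L: week-4 scores are collected but do not inform the week-8 arm comparison, which is in effect an observed-case test, less precise than it could be and open to bias if dropout differs by arm or follows a treatment effect

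*SAP*

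**What the plan says.** SAP 2.3 lists "Symptoms measured by CAT score and EQ-5D-5L from baseline to week 8" as a clinical exploratory outcome. The schedules in both documents place CAT and EQ-5D-5L at visits 1, 2 and 3. For week 4, Protocol 10.1.3 says "CAT and EQ-5D-5L assessments will be completed remotely via telephone call", and 10.1.4 arranges week 8 in the same way.

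The only arm comparison is in SAP 7.2: "The change from baseline to 8 weeks will analysed using independent t-test or non-parametric alternative". SAP 8.4 gives week 4 no inferential role: "Descriptive statistics will also be presented at baseline, week 4 and week 8, mean(SD), median (IQR) or n(%) by treatment arm". The shell table of exploratory outcomes has one difference and one p-value for each instrument. No repeated-measures model appears in either document.

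On adjustment, SAP 7 plans "t-tests followed by analysis of covariance adjusting for baseline FEV1 and other covariates if required" for continuous outcomes. FEV1 is the only covariate named; the baseline CAT or EQ-5D score is not mentioned.

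On missing data there are two rules. SAP 7 says "If necessary, these issues will be dealt with using multiple imputation or Bayesian methods for missing data as appropriate", after a review of the level, pattern and causes of missingness. SAP 3.4 says that missing clinical data will not be imputed, and expects little of it. SAP 5 inflates the sample size for about 30% dropout.

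**The concern.** A patient with a baseline and a week-4 score but no week-8 score cannot enter a two-sample test of week-8 change unless a value is imputed. The one unconditional rule, in SAP 3.4, forbids that. The rule in SAP 7 has no trigger and no imputation model. As written, the comparison therefore rests on patients with a week-8 score, and the week-4 information from those lost in between is unused.

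Two things are at stake. The first is precision: both the baseline score and the week-4 score predict week 8. The second is bias. If patients who feel worse at week 4 leave more often in one arm, or if the drug changes the symptoms that lead patients to leave, those who remain differ between arms for reasons other than the treatment effect at week 8. Quality of life is a stated exploratory objective, and a p-value will be printed for it.

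**Working it through.** **The plan's own figure.** The 30% comes from the sample size for EBV suppression (70% against 30%, two-sided 0.05, 90% power):

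n = [1.960 × √(2 × 0.5 × 0.5) + 1.282 × √(0.7 × 0.3 + 0.3 × 0.7)]² / 0.4² = (1.386 + 0.831)² / 0.16 = 30.7, so 31 per group, as stated.

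For dropout, 31/0.70 = 44.3; the plan uses 44, and 44 × 0.70 = 30.8. The figures reproduce to within rounding. No sample size is given for CAT or EQ-5D-5L.

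**Assumptions.** The documents give no SD or correlation for these scores, so these are assumed: SD 1 at each visit; correlations 0.7 (baseline with week 4), 0.7 (week 4 with week 8) and 0.6 (baseline with week 8); logistic dropout of about 30% in the reference arm, all of it after week 4. Bias was simulated with 1,000,000 patients per arm, and type I error with 44 per arm and 10,000 trials. The slope is the log-odds of dropout per SD of the score. The right-hand column is an estimate that also uses the baseline and week-4 scores of those lost.

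| Dropout depends on | True effect (SD) | Bias, planned test (SD) | Bias, using week 4 (SD) |
|---|---|---|---|
| week-4 change, same in both arms, slope 1 | 0 | 0.00 (type I error 0.049) | 0.00 |
| week-4 change, same in both arms, slope 1 | 0.5 | 0.03 | 0.00 |
| week-4 change, same in both arms, slope 2 | 0.5 | 0.07 | 0.00 |
| week-4 level, same in both arms, slope 1 or 2 | 0.5 | 0.00 | 0.00 |
| week-4 change, one arm only, slope 1 | 0 | 0.11 (type I error 0.073) | 0.00 |
| week-4 change, opposite directions by arm, slope 1 | 0 | 0.21 (type I error 0.157) | 0.00 |
| week-4 level, one arm only, slope 1 | 0 | 0.00 | 0.00 |
| unseen week-8 score, one arm only, slope 1 | 0 | 0.11 | 0.14 |

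The zeros for dropout on the week-4 level are a product of the assumed correlations. The covariance of (week 8 − baseline) with week 4 is 0.7 − 0.7 = 0, so selection on week 4 does not shift the mean change. Unequal correlations would remove this cancellation.

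**Cross-check of the type I error.** The variance of change is 2(1 − 0.6) = 0.80. With 31 per arm, SE = √(2 × 0.80/31) = 0.227 SD. A bias of 0.11 (0.105 unrounded) is 0.46 SE, giving P(Z > 1.50) + P(Z < −2.42) ≈ 0.075. A bias of 0.21 (0.214) is 0.94 SE, giving about 0.156. Both agree with the simulation.

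**Would covariate adjustment alone cure it?** No. An observed-case analysis of covariance on the baseline score still had bias of 0.07 SD (week-4 change, one arm) and 0.15 SD (opposite directions). It had 0.08 SD for week-4 level in one arm, where the change test had none.

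**Precision.** Adjusting for the baseline score gives residual variance 1 − 0.6² = 0.64 against 0.80 for change, a ratio of 0.80, or 20% lower. Given baseline, the squared correlation of week 4 with week 8 is (0.7 − 0.7 × 0.6)² / [(1 − 0.49)(1 − 0.36)] = 0.0784/0.3264 = 0.24. If 30% are lost after week 4 for reasons unrelated to symptoms, week 4 lowers the variance by a further 0.30 × 0.24 = 7%. Most of the gain comes from the baseline score; the protection against bias comes from week 4.

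**The case against.** The strongest reply has four parts.

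First, a reader might infer that the comparison is biased whenever dropout follows symptoms. That is not so. With the same symptom-driven mechanism in both arms and no effect, the bias is zero and the type I error is 0.049. Even with a 0.5 SD effect, a shared mechanism gives at most 0.07 SD in these scenarios. Nothing in the documents shows that dropout will differ by arm. This part stands, and it limits the point.

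Second, a reader might infer that the SAP declares a completer analysis. It does not: SAP 7 states intention-to-treat, promises to examine missingness, and allows multiple imputation, which could use week 4. This stands only in part, because the permission is conditional and unspecified and SAP 3.4 says the opposite. The observed-case reading is an inference from SAP 3.4 and 7.2 together.

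Third, a reader might take 30% as the expected loss of questionnaires. The documents set it for the EBV outcome. The questionnaires are taken by telephone, and Protocol 7.3 keeps patients who stop the drug in follow-up. For those who withdraw consent, however, 7.3 seeks only access to medical records, and the call four weeks after stopping (Protocol 10.1.5) covers adverse events and exacerbations but neither questionnaire. The true loss may be well below 30%, and the bias would shrink with it.

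Fourth, these outcomes are exploratory, with no power claim. Nor are they the only patient-relevant measures left now that lung function is no longer measured, since SAP 8.4 also compares exacerbations to week 12. This stands and sets the severity.

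**Conclusion.** The point holds as a minor one. Week-4 CAT and EQ-5D-5L scores are collected and do not inform the arm comparison, and two SAP sections give conflicting rules for missing values. Under the assumed correlations and about 30% dropout, the planned test has bias of about 0 to 0.2 SD when dropout is arm-specific (type I error up to about 0.16 in the most adverse case tried) and 0 to 0.07 SD when the mechanism is shared and the effect is 0.5 SD. It has none under the null with a shared mechanism. An analysis using baseline and week 4 had near-zero bias wherever dropout depended on observed scores, and a variance at least about 20% lower.

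These sizes depend on assumed correlations and slopes, and on all losses falling after week 4; patients lost earlier have no week-4 score to use. A reader might also infer that week-4 data would correct any symptom-driven dropout. They do not when dropout follows the unseen week-8 score (0.14 SD against 0.11 SD for the planned test).

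**What to change.** In SAP 7.2 and 8.4, compare CAT total, EQ-5D index and EQ-5D VAS with a mixed model for repeated measures on weeks 4 and 8. Terms: arm, visit, arm × visit, baseline score and baseline × visit, with unstructured covariance. Report the week-8 arm difference with its 95% CI, and keep the t-test of change as a supportive analysis. Protocol 13.2 already leaves room for other suitable methods for these outcomes.

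Reconcile SAP 3.4 with SAP 7: state whether missing questionnaire scores may be imputed and, if so, when and with which model. Add one simple not-at-random sensitivity analysis, for example shifting the unobserved week-8 scores by a stated range in each arm. If this is done by imputation, the wording of SAP 3.4 must permit it.

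The cost is SAP text, one standard model per outcome and a small change to the shell table of exploratory outcomes. No new data are needed. The model assumes that dropout is explained by observed scores, which is why the sensitivity analysis belongs with it.
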